Appendix 7. Cockcroft-Gault Method for Estimating Creatinine Clearance

Formulas for calculating the estimated creatinine clearance (eC_{cr}) are provided in the table below. The formula appropriate to the units in which serum creatinine was measured and the subject's gender should be used.

Serum Creatinine Units	Gender	Formula
mg/dL	Males	$eC_{cr} \text{ [mL/min]} = \frac{(140 - \text{subject age [years]}) \times \text{subject weight [kilograms]} \times 1}{72 \times \text{subject serum creatinine [mg/dl]}}$
	Females	$eC_{cr} \text{ [mL/min]} = \frac{(140 - \text{subject age [years]}) \times \text{subject weight [kilograms]} \times 0.85}{72 \times \text{subject serum creatinine [mg/dl]}}$
μmol/L	Males	$eC_{cr} \text{ [mL/sec]} = \frac{(140 - \text{subject age [years]}) \times \text{subject weight [kilograms]}}{[(72 \times \text{serum creatinine } (\mu\text{mol /L}) \times 0.6786]}$
	Females	$eC_{cr} \text{ [mL/sec]} = \frac{(0.85 \times (140 - \text{subject age [years]}) \times \text{subject weight [kilograms]}}{[(72 \times \text{serum creatinine } (\mu\text{mol /L}) \times 0.6786]}$

eC_{cr}=estimated creatinine clearance

Appendix 8. Pandemic Risk Assessment and Mitigation Plan

During an ongoing pandemic, potential risks associated with subjects being unable to attend study visits have been identified for this study.

These potential risks and mitigation plans can be summarized as follows:

1) Subject screening and enrollment

- a) Prior to screening and enrolling any new subjects, the site monitor will confirm
 - i) The site is able to perform protocol-required procedures and data collection by delegated/trained staff.
 - ii) The site is able to adequately manage the subject's safety in light of COVID-19; and they should only proceed with screening if there are no known issues that may impact the ability for the subject to attend study visits.
 - iii) The principal investigator (PI) deems study participation and onsite visits outweigh the risk of COVID-19 exposure.

2) Study drug supplies to subjects and sites

- a) Subjects may be unable to return to the site for a number of visits to get the study drug, or the site may be unable to accept any subject visits. Without study drugs, the subject would not be able to stay on the study drug as planned per protocol.

Mitigation plan:

- i) Study drug supplies may be provided to the subject from the site without a clinic visit, once it is confirmed that the subject may safely continue on study drug as determined by the PI.
- ii) A virtual study visit, via phone or video conferencing, must be performed prior to remote study drug resupply. At the earliest opportunity, the site will schedule in-person subject visits and return to the protocol's regular schedule of assessments.
- iii) A qualified courier may be utilized to ship the study drug from sites to study subject's home if permitted by local ethic committee (EC)/institutional review boards (IRB)/Regulatory Authority as applicable and with sponsor's approval.
- iv) Obtain subject's consent verbally (eg, by phone) to ship investigational medicinal product (IMP) from site to the subject's home and to provide the subject's address to the courier service responsible for delivering the IMP. The date and time that the consent was obtained must be documented in the subject's source documents.
- v) Ensure IMP documentation is complete for the shipment from site to subject.

- vi) Utilize same day or overnight shipping with tracking information. Provide a clear chain of custody.
- b) Shipments of study drug could be delayed because of transportation issues. Without study drug subject would not be able to stay on the study drug as planned per protocol.

Mitigation plan The study drug supply lookout window was increased to 90 days for all drug shipments to mitigate the risk of insufficient study drug supply or shipment delays from the depot to the study site.

- i) All sites with active subjects to confirm capacity to store the extra supply of study drug prior to shipment.
 - ii) The sites' study drug inventory should be closely monitored. Site staff should notify the sponsor or delegate if they foresee shortage in study drug inventory or if there is any interruption in local shipping service.
 - iii) The sponsor will continue to monitor inventory at the study drug depot and study sites. Manual shipments will be triggered as necessary.
- 3) Subject safety monitoring and follow-up:
- a) Subjects may be unable or unwilling to come to the study site for their scheduled study visits as required per protocol.

Mitigation plan: For subjects who may be unable or unwilling to visit the study site for their scheduled study visits as required per protocol, the PI or qualified delegate will conduct a virtual study visit, via phone or video conferencing, to assess the subject within target visit window date whenever possible. During the virtual study visit, the following information at minimum will be reviewed:

- i) Confirm if subject has experienced any adverse events (AEs)/serious adverse events (SAEs)/special situations (including pregnancy) and follow-up on any unresolved AE/SAEs.
- ii) Review current list of concomitant medications and document any new concomitant medications.
- iii) Confirm if subject dosing diary questionnaires is completed.
- iv) Confirm subject's study drug supply is sufficient to last until the next planned visit date. If study drug resupply is needed it will be provided as described above in (2).
- v) Remind subject to maintain current dosing and to keep all dispensed study drug kits for return at the next on-site visit.

vi) If more than one visit will be missed, and other local labs or alternatives are not possible, please discuss ongoing subject participation with the medical monitor.

- b) Subjects may be unable or unwilling to travel to the site for planned assessments (eg, safety blood draws); hence samples may not be sent for central lab analyses.

Mitigation plan: Local labs may be utilized as appropriate to monitor subject safety until the subject can return to the site for their regular follow-up per protocol. Any laboratory assessments conducted at a local lab due to the pandemic will be documented accordingly. Pregnancy testing may be performed using a home urine pregnancy test if local lab pregnancy testing is not feasible. A positive urine pregnancy test must be immediately confirmed with a serum pregnancy test. If serum pregnancy test is positive, please see instructions for reporting pregnancy in Section 7.6.2.1 of this document.

- c) Subjects may be unable or unwilling to attend the study visit to sign an updated informed consent form version.

Mitigation plan: The site staff will follow their approved consent process and remain in compliance with local EC/IRB and national laws and regulations. Remote consent will be allowed if it has been approved by the local EC/IRB. The consent process will be documented and confirmed by normal consent procedure at the earliest opportunity.

- d) The safety of trial participants is important and testing of COVID-19 infection will be based on local clinical guidelines for testing based on signs/symptoms and or suspected exposure to COVID-19.

Mitigation Plan: If subject becomes infected with COVID-19 while on study, please inform the Contract Research Organization and Gilead immediately. If test results are positive for COVID-19, consider discontinuing or interrupt idelalisib until patient has clinically recovered. Discuss with the medical monitor prior to resuming study drug or if subject becomes COVID-19 negative.

COVID-19 infections including asymptomatic infections or positive tests for COVID-19, should have this recorded as an AE. Any AEs attributed to COVID treatments should also be recorded in the electronic data capture, regardless of causality.

4) Protocol and monitoring compliance:

- a) Protocol deviations may occur, in case scheduled visits cannot occur as planned per protocol.

Mitigation plan: If it is not possible to complete a required procedure, an unscheduled visit should be conducted as soon as possible when conditions allow. The situation should be recorded and explained as a protocol deviation. Any missed subject visits or deviation to the protocol due to the pandemic must be reported in the eCRF and described in the

clinical study report. Any virtual study visits that are conducted in lieu of clinic visits due to the pandemic will be documented as a protocol deviation related to the pandemic.

- b) Study monitors may be unable to carry out source data review or source data verification (SDV), or study drug accountability or assess protocol and Good Clinical Practice compliance. This may lead to delays in SDV, an increase in protocol deviations, or under reporting of AEs.

Mitigation plan: The study monitor is to remain in close communication with the site to ensure data entry and query resolution. Remote SDV may be arranged if allowed. The study monitor is to reference the Clinical Management Plan for guidance on how to conduct a remote monitoring visit. The study staff is to save and document all relevant communication in the study files. The status of sites that cannot accept monitoring visits and/or subjects on site, must be tracked centrally and updated on a regular basis.

5) Missing data and data integrity:

- a) There may be an increased amount of missing data due to subjects missing visits/assessments. This could have an impact on the analysis and the interpretation of clinical trial data.

Mitigation plan: Implications of a pandemic on methodological aspects for the study will be thoroughly assessed and documented, and relevant actions will be taken as appropriate (ie, modification of the statistical analysis plan) and in compliance with Regulatory Authorities' guidance. Overall, the clinical study report will describe the impact of the pandemic on the interpretability of study data.

Risks will be assessed continuously, and temporary measures will be implemented to mitigate these risks as part of a mitigation plan, as described above. These measures will be communicated to the relevant stakeholders as appropriate and are intended to provide alternate methods that will ensure the evaluation and assessment of the safety of subjects who are enrolled in this study.

Since these potential risks are considered mitigated with the implementation of these measures, the expected benefit-risk assessment of idelalisib in study subjects remains unchanged.

1. INTRODUCTION

This statistical analysis plan (SAP) describes the statistical analysis methods and defines key elements including variable definitions for analysis of data of Study *GS-US-313-1580* in support of the clinical study report (CSR). This SAP is based on the study protocol *amendment 6* dated *18 March 2021*. Any changes made after the finalization of the SAP will be documented in the CSR.

This study was designed to evaluate a safe and effective dosing regimen of idelalisib in subjects with relapsed or refractory Follicular Lymphoma (FL) who have no other therapeutic options. It is a randomized, open-label, multi-center global study with three treatment arms in total of 266 subjects planned. The study was terminated early due to slow enrollment, with rapidly evolving treatment options for FL as the primary reasons.

Analysis methods specified in this document take precedence over those described in protocol should there be any difference.

1.1. Study Objectives

1.1.1. Primary Objectives

- Establish a safe and effective dosing regimen of idelalisib in subjects with relapsed or refractory FL who have no other therapeutic options

1.1.2. Secondary Objectives

- Evaluate the overall response rate (ORR)
- Evaluate the progression-free survival (PFS), duration of response (DOR), and overall survival (OS)
- Evaluate the overall safety profile of idelalisib
- Determine the PK of idelalisib and its major metabolite (GS-563117)

1.2. Study Endpoints

1.2.1. Primary Endpoints

- ORR, defined as the proportion of subjects who achieve a partial response (PR) or complete response (CR) by independent review committee (IRC)
- Incidence of Grade ≥ 4 treatment-emergent adverse events (TEAEs)

1.2.2. Secondary Endpoints

- DOR, defined as the interval from the first documentation of CR or PR to the earlier of the first documentation of disease progression by independent review committee (IRC or death from any cause
- ORR by Week 24, defined as the proportion of subjects who achieve a PR or CR by Week 24
- Overall safety profile of idelalisib, including the incidence of AEs and clinically significant laboratory abnormalities, severity, timing, and relationship to idelalisib of any AEs; SAEs; or AEs leading to interruption, reduction, or discontinuation of idelalisib Time to onset of AEs of interest (AEIs) defined as the interval from the start of idelalisib treatment to the first documentation of start of AEI
- PFS, defined as the interval from randomization to the earlier of the first documentation of disease progression by IRC or death from any cause
- OS, defined as the interval from randomization to death from any cause
- Idelalisib trough (predose) and peak (1.5-hour samples) plasma concentrations assessed by validated bioanalytical method

1.3. Study Design

This is a randomized, open-label, multi-center study that will be conducted globally.

Subjects will be randomized in a 1:1 ratio, until the enrollment target per arm is met, to the following treatment arms:

- Arm A: 150 mg twice daily idelalisib administered continuously
- Arm C: 150 mg twice daily idelalisib administered in 28-day cycles (21 days on-treatment, 7 days off-treatment)

[figure not shown]
The original protocol for this study included an Arm B, which was closed to enrollment as of Protocol Amendment 5.

- Arm B (*closed to enrollment as of Protocol Amendment 5*): 100 mg twice daily idelalisib administered continuously

[figure not shown]
Clinic visits will occur at Screening, Day 1, every 2 weeks through Week 12, every 4 weeks through Week 24, at Weeks 32, 36, 40, 48, and every 12 weeks thereafter through end of study (EOS). Subjects will be assessed for safety at each visit. Additional visits will be required between clinic visits for laboratory testing only.

Subjects will be assessed for FL disease status by continuous utilization of a single modality including positron emission tomography–computed tomography (PET-CT), CT, or MRI. If permanent discontinuation of idelalisib occurs prior to IRC documented progression of FL, subjects shall remain on study until progression of FL or withdrawal from the study for reasons specified in Section 3.5.2 of the Protocol Amendment 6.

Figure 1-1. Study Schema

Subjects enrolled prior to implementation of Protocol Amendment 5 followed the previous study design as shown here.

* Unblinding and dose modifications may occur at any time during study participation if the IRC Assessment confirms progressive disease.

In accordance with Protocol Amendment 6, subjects enrolled prior to implementation of Protocol Amendment 5 and still blinded will be unblinded at the time of Protocol Amendment 6 implementation; these subjects will continue at the randomized dose level if they are still on treatment. These subjects were previously randomized in a blinded manner to either 150 mg twice daily or 100 mg twice daily idelalisib. Based on the 8-week blinded IRC response assessment, subjects with SD or PD were unblinded in both arms. Subjects with a PR or CR maintained the blind and continued at the randomized dose level. Subjects randomized to 100 mg twice daily with SD or PD had the option to be dose escalated to 150 mg twice daily. Subjects randomized to 150 mg twice daily with SD will continue open-label idelalisib at 150 mg twice daily. Subjects randomized to 150 mg twice daily with PD will be discontinued from study treatment. These same unblinding and dose modification principles were applied at any time throughout study participation when disease progression was suspected and confirmed by IRC assessment.

Subjects should follow study procedures as outlined in Section 6 and Appendix 2 Study Procedures Table of the Protocol Amendment 6. Idelalisib will be administered until meeting criteria for discontinuation of study drug as described in Section 3.5.1 of the protocol Amendment 6.

1.4. Sample Size

The planned sample size is approximately 266 subjects: approximately 120 subjects in Arm A, approximately 26 subjects in Arm B, and approximately 120 subjects in Arm C. As of Protocol Amendment 5, Arm B enrollment was closed after enrollment of approximately 26 subjects into Arm B and approximately 26 subjects into Arm A.

As of Protocol Amendment 5, subjects will be randomized to 2 arms (Arms A and C) with a 1:1 ratio until the enrollment target of 120 subjects in each arm is met. The ORR was approximately 56% for subjects with FL in Study 101-09. If the underlying true ORR is 56% for subjects in this study, the chance to observe 60 or more responders out of 120 subjects (observed ORR \geq 50%) is 92%. With 120 subjects in each arm, the half-width of a two-sided 95% CI of ORR is \leq 10% for an observed ORR in the range of 40%-60%, and the half-width of a two-sided 95% CI of \geq Grade 4 TEAEs incidence rate is \leq 10% for an observed AE rate in the range of 20%-40%.

The sample size was originally planned to include 240 subjects randomized to Arm A and Arm B with a 1:1 ratio. The previous sample size calculation is based on the rate of Grade \geq 3 diarrhea/colitis at approximately 15% in the prior idelalisib studies. A sample size of 120 subjects per arm would provide 73% chance to detect a reduction of 10% (ie, 15% incidence in the 150 mg twice daily arm versus 5% incidence in the 100 mg twice daily arm) using a 2-sided Chi-square test with alpha level of 0.05.

2. PLANNED ANALYSIS

2.1. Data Monitoring Committee (DMC) Analysis

An external multidisciplinary DMC will review the progress of the study and perform interim reviews of safety data at regular intervals until all blinded subjects are either unblinded or off the study. The DMC will provide recommendations to Gilead as to whether the nature, frequency, and severity of adverse effects associated with study treatment warrant the early termination of the study in the best interests of the study participants, whether the study should continue as planned, or whether the study should continue with modifications.

The DMC's specific activities will be defined by a mutually agreed charter, which will define the DMC's membership, conduct, and meeting schedule.

CCI

2.2. Primary Analysis

The primary study analysis will be conducted when all enrolled subjects have discontinued the study or been on treatment for at least 48 weeks and completed response assessment of Week 48.

2.3. Final Analysis

The final analysis will be performed after all subjects have completed or discontinued from the study, outstanding data queries have been resolved or adjudicated as unresolvable, and the data have been cleaned and finalized.

3. GENERAL CONSIDERATIONS FOR DATA ANALYSES

Analysis results will be presented using descriptive statistics. For categorical variables, the number and percentage of subjects in each category will be presented; for continuous variables, the number of subjects (n), mean, standard deviation (StD) or standard error (SE), median, first quartile (Q1), third quartile (Q3), minimum, and maximum will be presented.

By-subject listings will be presented for all subjects in the All Enrolled Analysis Set and sorted by dose cohort, subject ID number, visit date, and time (if applicable). Data collected on log forms, such as AEs, will be presented in chronological order within the subject. The cohort to which subjects were initially assigned will be used in the listings. Age, sex at birth, race, and ethnicity information for each subject will be presented in the listings, as space permits.

3.1. Analysis Sets

Analysis sets define which subjects are included in an analysis. Analysis sets and their definitions are provided in this section. The analysis set will be identified and included as a subtitle of each table, figure, and listing.

3.1.1. All Enrolled Analysis Set

The All Enrolled Analysis Set includes all subjects who received a study subject identification number in the study after screening.

The All Enrolled Analysis Set will be used for subject enrollment summary and for data listings, unless otherwise specified.

3.1.2. Intent-to-Treat (ITT) Analysis Set

The ITT Analysis Set includes all subjects who are randomized regardless of whether subjects receive any study drug. Treatment assignment will be designated according to a subject's initial randomization. This analysis set will be used in the analysis of efficacy.

3.1.3. Safety Analysis Set

The Safety Analysis Set includes all subjects who received at least 1 dose of study treatment, with treatment assignments designated according to the actual treatment received. This is the primary analysis set for the safety analyses as well as study treatment administration.

3.1.4. Pharmacokinetics (PK) Analysis Set

The PK Analysis Set includes subjects in the Safety Analysis Set who have received the study drug and have at least 1 sample with detectable drug concentration.

3.2. Subject Grouping

For analyses based on the ITT Analysis Set, subjects will be grouped according to the treatment to which they were randomized. For analyses based on the Safety Analysis Set, subjects will be grouped according to the actual treatment received. The actual treatment received will differ from the randomized treatment only when their actual treatment differs from randomized treatment for the entire treatment duration.

For the PK Analysis Set, subjects will be grouped according to the actual treatment they received.

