1.3. Rationale for This Study

Zydelig[®] (idelalisib) received accelerated approval in the US for the treatment of patients with relapsed FL who have received at least 2 prior systemic therapies based on results from a single-arm study (101-09) in 125 subjects with iNHL, including 72 subjects with FL, who had relapsed within 6 months following rituximab and an alkylating agent and had received at least 2 prior treatments. In Study 101-09, all subjects received idelalisib 150 mg twice daily, with dose reductions to 100 mg twice daily allowed during the study to manage toxicity, consistent with the subsequently approved Zydelig[®] dosing regimen. The present study, GS-US-313-1580, is being conducted as a US postmarketing requirement (PMR 2180-10) under the accelerated approval regulations to verify the clinical benefit of Zydelig[®] monotherapy in patients with relapsed or refractory FL.

The subject population to be enrolled under the original version of this protocol comprised patients with previous systemic treatment for FL or SLL. In 2016, following identification of a safety signal and termination of several ongoing studies evaluating idelalisib in unapproved combinations (see Section 1.4, Anticipated Risks), the subject population in this study was restricted to align with the Zydelig[®] EU Summary of Product Characteristics while the European Medicines Agency Pharmacovigilance Risk Assessment Committee conducted a review under Article 20 of Regulation (EC) No 726/2004. The outcome of the Article 20 procedure confirmed a positive risk-benefit profile in the approved Zydelig[®] indications. Following discussions with the Food and Drug Administration (FDA) regarding this postmarketing study requirement, and a careful benefit-risk evaluation, the eligible subject population in Protocol Amendment 5 is being modified to include patients with relapsed or refractory FL who have received at least 2 lines of prior therapy for FL, have no other therapeutic options, and require therapy according to standard response criteria.

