As of Protocol Amendments 5 and 6, this open-label study will evaluate the approved dosing regimen of 150 mg twice daily (Arm A) and an alternative dosing regimen (Arm C), with the goal of assessing whether the efficacy of the approved dosing regimen could be confirmed and alternative dosing regimen can achieve similar efficacy as the approved dosing regimen with reduced toxicity. Arm A will utilize the standard dosing schedule of continuous idelalisib administered twice daily. Subjects in Arm C will receive idelalisib at the approved dose of 150 mg twice daily for the first 21 days of each 28-day cycle, followed by 7 days off treatment.

As of Protocol Amendment 6, there will be a planned global unblinding of all blinded subjects.

In addition to the aforementioned efficacy assessments, this study will assess the incidence of Grade ≥ 4 treatment-emergent adverse events (TEAEs) in each treatment arm. Of the 72 subjects with FL in Study 101-09, 23 subjects (32%) reported at least 1 Grade ≥ 4 TEAE, most frequently neutropenia (5 subjects [7%]), hypokalaemia (3 subjects [4%]), infections (2 subjects [3%]), increased aspartate aminotransferase (AST) (2 subjects [3%]), and thrombocytopenia (2 subjects [3%]).

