3.2.1. Study Schema

Figure 3-1. Study Schema

3.2.2. Subjects Enrolled Prior to Protocol Amendment 5

Subjects enrolled prior to implementation of Protocol Amendment 5 followed the previous study design as shown here.

* Unblinding and dose modifications may occur at any time during study participation if the IRC Assessment confirms progressive disease.

In accordance with Protocol Amendment 6, subjects enrolled prior to implementation of Protocol Amendment 5 and still blinded will be unblinded at the time of Protocol Amendment 6 implementation; these subjects will continue at the randomized dose level if they are still on treatment. These subjects were previously randomized in a blinded manner to either 150 mg twice daily or 100 mg twice daily idelalisib. Based on the 8-week blinded IRC response assessment, subjects with SD or PD were unblinded in both arms. Subjects with a PR or CR maintained the blind and continued at the randomized dose level. Subjects randomized to 100 mg twice daily with SD or PD had the option to be dose escalated to 150 mg twice daily. Subjects randomized to 150 mg twice daily with SD will continue open-label idelalisib at 150 mg twice daily. Subjects randomized to 150 mg twice daily with PD will be discontinued from study treatment. These same unblinding and dose modification principles were applied at any time throughout study participation when disease progression was suspected and confirmed by IRC assessment.

Subjects should follow study procedures as outlined in Section 6 and Appendix 2 Study Procedures Table. Idelalisib will be administered until meeting criteria for discontinuation of study drug as described in Section 3.5.1.

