8.8. Sample Size

The planned sample size is approximately 266 subjects: approximately 120 subjects in Arm A, approximately 26 subjects in Arm B, and approximately 120 subjects in Arm C. As of Protocol Amendment 5, Arm B enrollment was closed after enrollment of approximately 26 subjects into Arm B and approximately 26 subjects into Arm A.

As of Protocol Amendment 5, subjects will be randomized to 2 arms (Arm A and C) with a 1:1 ratio until the enrollment target of 120 subjects in each arm is met. The ORR was approximately 56% for subjects with FL in Study 101-09. If the underlying true ORR is 56% for subjects in this study, the chance to observe 60 or more responders out of 120 subjects (observed $ORR \geq 50\%$) is 92%. With 120 subjects in each arm, the half-width of a two-sided 95% CI of ORR is $\leq 10\%$ for an observed ORR in the range of 40%-60%, and the half-width of a two-sided 95% CI of \geq Grade 4 TEAEs incidence rate is $\leq 10\%$ for an observed AE rate in the range of 20%-40%.

The sample size was originally planned to include 240 subjects randomized to Arm A and Arm B with a 1:1 ratio. The previous sample size calculation is based on the rate of Grade ≥ 3 diarrhea/colitis approximately 15% in the prior idelalisib studies. A sample size of 120 subjects per arm would provide 73% chance to detect a reduction of 10% (ie, 15% incidence in the 150 mg twice daily arm versus 5% incidence in the 100 mg twice daily arm) using a 2-sided Chi-square test with alpha level of 0.05.

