3.4. Examination of Subject Subgroups

There are no prespecified subject subgroupings for efficacy and safety analyses.

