6.1.2. Analysis for Secondary Endpoints

The ORR by Week 24 and corresponding 95% CIs will be evaluated by treatment arm using the IRC assessments in the ITT Analysis Set.

The time-to-event efficacy endpoints including PFS, DOR, and OS will be analyzed using the Kaplan-Meier method in the ITT Set, and the analysis of DOR will include subjects who achieve a PR or CR. Analyses may also be performed for subgroups defined by potential predictors of response. The Kaplan-Meier plot will be provided for PFS and OS.

PFS and DOR Censoring rules:

- 1) Subjects who discontinued study prior to PD or death will be censored on the last tumor assessment date.
- 2) Subjects who missed ≥ 2 consecutive tumor assessments, and did not have a PD prior to missing ≥ 2 consecutive tumor assessments will be censored on the last tumor assessment date prior to missing ≥ 2 consecutive assessments.
- 3) Subjects who received new anti-cancer therapy will be censored on the last assessment date prior to receiving new anti-cancer therapy.
- 4) Subjects who are alive and do not have any on-study tumor assessments will be censored on the randomization date (applicable only for PFS)

OS censoring rules:

- 1) Subjects who do not have a recorded death date will be censored on the last known alive date.

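### The primary Grade ≥ 4 TEAE rate is reported without the 95% CI that the sample size was built on, and Arm A includes about 26 subjects who are not concurrent controls for Arm C

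*SAP*

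**What the plan says.** SAP 1.2.1 names two primary endpoints: ORR by IRC and the incidence of Grade ≥ 4 TEAEs. SAP 1.4, like protocol 8.8, supports 120 per arm by a 95% CI half-width of at most 10 points for ORR between 40% and 60% and for the TEAE rate between 20% and 40%.

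The two endpoints are then reported differently. SAP 6.1.1 gives ORR a Clopper-Pearson 95% CI. SAP 3 and 7.1.6.1 give the TEAE summaries, including Grade 4 or higher, as number and percentage. Protocol 8.6.2 also asks only for number and percentage, but protocol 8.3 says percentages will typically carry exact 95% CIs. SAP 1 says the SAP prevails where the two differ.

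On grouping, SAP 3.2 states: "For analyses based on the ITT Analysis Set, subjects will be grouped according to the treatment to which they were randomized". Safety analyses group by actual treatment. SAP 3.3 has no strata or covariates, and SAP 3.4 says: "There are no prespecified subject subgroupings for efficacy and safety analyses". SAP 6.1.2, on time-to-event endpoints, adds: "Analyses may also be performed for subgroups defined by potential predictors of response". It does not mention enrolment period.

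On the composition of Arm A, protocol 8.8 says: "Arm B enrollment was closed after enrollment of approximately 26 subjects into Arm B and approximately 26 subjects into Arm A". SAP 1.3 says of the subjects enrolled before Amendment 5: "These subjects were previously randomized in a blinded manner to either 150 mg twice daily or 100 mg twice daily idelalisib".

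On the A-versus-C question, the protocol 1.3 rationale describes what the study set out to learn from Amendment 5 onward: "efficacy of the approved dosing regimen could be confirmed and alternative dosing regimen can achieve similar efficacy as the approved dosing regimen with reduced toxicity".

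**The concern.** There are two separate gaps.

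First, the trial was sized so that the Grade ≥ 4 TEAE rate would be known to within 10 points, but no table is planned that shows how precisely it is known. SAP 1 records that the study stopped early for slow enrolment, so the planned precision may not have been reached. A bare percentage would not show that.

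Second, the early Arm A subjects differ from the later ones in documented ways:

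- **Eligibility.** Protocol 1.3 says "the eligible subject population in Protocol Amendment 5 is being modified to include patients with relapsed or refractory FL", with further conditions on prior therapy and options.
- **Scans.** Protocol 6.1.7 puts early scans at Weeks 8, 16 and 24 for the first group, and at Weeks 12 and 24 for the later group.
- **Blinding.** The early group started blinded with matched placebo (protocol 5.1). Then, per protocol 3.2.2, "Based on the 8-week blinded IRC response assessment, subjects with SD or PD were unblinded in both arms". Later subjects were open-label throughout.

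Only subjects randomised while A and C were both open are protected by randomisation for an A-versus-C reading. The planned tables put a mixed-period Arm A column beside Arm C and give no means of separating the periods.

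**Working it through.** **1. The plan's own figures.** Inputs from SAP 1.4: n = 120, true ORR 56%, at least 60 responders.

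- P(X ≥ 60 | n = 120, p = 0.56) = 0.921. Stated 92%; reproduces.
- Clopper-Pearson limits for x of n: L = Beta⁻¹(0.025; x, n−x+1) and U = Beta⁻¹(0.975; x+1, n−x). Half-width = (U−L)/2.
- Largest half-width at n = 120: 9.3 points for ORR (48 to 72 responders) and 9.1 points for TEAE (24 to 48 subjects). Stated at most 10; reproduces.

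The sizing is correct. The gap lies in what is reported.

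**2. Precision of the TEAE rate if an arm is smaller.** The reference rate is 23/72 = 32% (Study 101-09, protocol 1.3). The documents give no enrolled total, so every n below 120 is an assumption.

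| x/n | 95% CI | Half-width (points) |
|---|---|---|
| 38/120 | 23.5–40.8% | 8.65 |
| 32/100 | 23.0–42.1% | 9.53 |
| 29/91 | 22.5–42.5% | 9.99 |
| 29/90 | 22.8–42.9% | 10.07 |
| 26/80 | 22.4–43.9% | 10.72 |
| 15/46 | 19.5–48.0% | 14.24 |

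Near 32% the 10-point limit is lost at n = 90 or fewer. At n = 99 the half-width runs from 8.33 at the low end of the 20%–40% range to 10.002 near 40%, and is 9.60 at 32/99. So at 99 or fewer the limit no longer holds at every rate in the range, and it fails first near 40%.

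**3. Early share of Arm A.** The plan totals 120 + 26 + 120 = 266, so the 120 in Arm A include the 26 early subjects. With m later Arm A subjects, share = 26/(26+m). If the early rate differs from the later rate by d, the pooled Arm A rate differs from the later rate by share × d. The documents give no d, and every m below 94 is assumed.

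| m | Share | Shift, d = 5 | d = 10 | d = 20 |
|---|---|---|---|---|
| 94 (plan) | 21.7% | 1.1 | 2.2 | 4.3 |
| 60 | 30.2% | 1.5 | 3.0 | 6.1 |
| 40 | 39.4% | 2.0 | 3.9 | 7.9 |
| 20 | 56.5% | 2.8 | 5.7 | 11.3 |

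**4. Precision of a concurrent A-versus-C difference.** With equal true rates and n per arm, half-width = 1.96 × √(2p(1−p)/n). Rates are 56% (ORR) and 32% (TEAE), from protocol 8.8 and 1.3. The 94 v 94 case infers from 1:1 allocation that 120 − 26 = 94 Arm A subjects were matched by 94 in Arm C.

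| n per arm | ORR | TEAE |
|---|---|---|
| 94 | 14.2 | 13.3 |
| 60 | 17.8 | 16.7 |
| 40 | 21.8 | 20.4 |
| 20 | 30.8 | 28.9 |

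Miettinen-Nurminen intervals at equal observed rates agree to within about a point. At every n shown, this uncertainty exceeds the shift from an assumed 10-point period difference.

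**The case against.** The case against has five parts.

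- **The SAP follows the protocol's endpoint text.** Protocol 8.6.2 asks for number and percentage, and SAP 7.1.6.1 delivers that. This stands: a reader who infers that the SAP departs from the endpoint definition would be wrong. But the CI is the stated basis for the sample size, and protocol 8.3 would typically have supplied it.
- **Anyone can compute the CI from the count.** True, and it keeps the point modest. It does not explain why one primary endpoint gets an interval and the other does not.
- **The A-versus-C question is not an objective.** It appears only in the protocol 1.3 rationale, not among the objectives or endpoints. No margin or comparative power is given for A versus C, and SAP 3.5 plans no formal testing. This stands. A reader might infer that the SAP fails a formal objective by omitting the contrast; the documents do not support that. A descriptive difference with a CI is nevertheless compatible with SAP 3.5.
- **Pooling Arm A is valid for what is planned.** This stands. A reader might infer that the planned Arm A results are biased, or that the ITT sentence is the defect. Neither follows. Non-concurrency matters only when Arm A is read against Arm C. The IRC reads without treatment assignment, and both scan schedules share Week 24 onward.
- **No period difference is shown.** Correct. Its size and direction are unknown, and the 5, 10 and 20 points are assumptions. By-subject listings and consent dates would let a reader approximate period, but they are not a planned summary.

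**Conclusion.** The concern holds in a limited form and should be fixed.

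The firmer part is the missing interval: a primary endpoint whose CI width justifies the sample size is planned without a CI. The second part is that about 26 Arm A subjects, 21.7% at plan and up to 56.5% if only 20 more enrolled, are not concurrent with Arm C and cannot be separated in the planned tables.

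Three limits apply. One might infer that at 99 or fewer subjects the 10-point precision is lost at every rate from 20% to 40%. It is not: at n = 99 it fails only near 40%, and near 32% it holds down to 91. Any loss of precision would come from enrolment, not from the SAP; the SAP's part is not showing it. The A-versus-C estimate is an improvement rather than the repair of a broken objective, and it cannot establish similar efficacy.

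The textual findings rest on the documents alone. The magnitudes assume the Study 101-09 rates, the approximate count of 26, and the stated range of arm sizes.

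**What to change.** 1. In SAP 7.1.6.1, add a Clopper-Pearson 95% CI to the per-arm percentage of subjects with at least one Grade ≥ 4 TEAE.
2. Keep the all-Arm-A estimates as planned. For any A-versus-C reading, report ORR and Grade ≥ 4 TEAE for Arm A subjects randomised from Amendment 5 on, beside Arm C. Give the A-versus-C difference with a 95% CI (for example Miettinen-Nurminen), restricted to subjects randomised while both arms were open, labelled descriptive and without a test.
3. State in the CSR that these summaries were added after early termination. SAP 1 already sends changes made after finalisation there.

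The cost is wording and a few table rows or columns. Randomisation dates exist, since SAP 6.1.2 uses them for PFS censoring, so no new data are needed. The downside is imprecision: a half-width of about 13 to 14 points at 94 v 94 and about 29 to 31 at an assumed 20 v 20. The table should warn against reading a wide interval that includes zero as evidence of similarity.
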